Title: Efficacy of the Quell Wearable Device for Chronic Low Back Pain

NCT# 02944513

Date: July 1, 2016

STUDY PROTOCOL - METHODS

This trial is registered at ClinicalTrials.gov (NCT02944513). The Human Subjects Committee of Brigham and Women's Hospital (BWH) will approve the study procedures and written informed consent will be obtained from every participant. Flyers will be distributed about this trial and subjects will be recruited consecutively as they respond to the flyers. We will recruit patients with a primary complaint of chronic low back pain and randomize each of the subjects to one of two treatment conditions: 1) the hTENS device or 2) treatment-as-usual control (no device) using a random number table (<https://www.graphpad.com/quickcalcs/randomize1.cfm>). All participants will be adults age 21 or older and diagnosed with axial musculoskeletal or discogenic back pain with or without radiculopathy. There will be a number of other inclusion criteria: (1) participants will need to own a compatible smartphone, either Android or iPhone, (2) they will have to have evidence of chronic pain for over 6 months and average ≥ 4 on a 0-10 pain intensity scale, and (3) they will need to understand and speak English. Study exclusion criteria will include (1) diagnosis of cancer, (2) evidence of osteomyelitis, (3) a psychiatric disorder judged to interfere with the study (e.g., psychosis or delusional disorder), (4) an active substance abuse disorder (e.g., cocaine or heroin use), (5) surgery scheduled within 3 months, (6) pregnancy, (7) an implanted device (e.g., pacemaker), and (8) any unstable systemic illness judged to interfere with treatment.

During the 3-month study period all participants will be discouraged from making changes in their pain management regimen.

We will employ the use of a smartphone pain app in this study,^{16,17} which was designed to collect daily assessment data as well as demographic and medical information. It was devised to help monitor daily patient progress over the period of the trial. All subjects will be informed how to find the apps ('Quell Relief' and 'BWH Painapp' either on the App Store or Google Play) and will be assisted in downloading the apps, if assistance is needed. The pain app has built-in daily reminders for the user with push notification to complete daily assessments as well as 2-way messaging to connect with study staff.

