Patients will be randomized to either the Experimental group with use of a hfTENS or Control group with treatment as usual. Both groups will be asked to use the smartphone pain app to monitor their daily assessments. All subjects will complete a packet of validated questionnaires and will be followed for 3 months. All participants will sign an informed consent form and will be given assistance in downloading the apps by a research assistant (RA) who will answer any questions and help to manage any problems that the individuals might encounter. All participants will be also administered QST at baseline.^{11,12}

Patients randomized to the experimental group (hfTENS) will be encouraged to use the device at least two hours every day. Tracking of use of the device will be available electronically through the hfTENS app. All demographic and daily pain assessment data will be stored on a secure server (Veracode tested) and messages will be sent via the 2-way messaging pain app program to help track use of the device and

to address any problems that the subjects might encounter. All subjects will be also asked to complete post-intervention mailed assessments after 3 months and return the completed assessments in pre-addressed stamped envelopes. Each subject will be compensated \$25 at baseline and \$50 at study completion upon receipt of their completed assessments. All subjects will be allowed to keep their hFTENS device at the end of the study. Those subjects assigned to the Control condition will be offered a hFTENS device at the end of the 3-month trial period.

Brief Quantitative Sensory Testing

Pressure pain thresholds (PPTs) will be assessed using a standard manual pressure algometer (*Wagner Force Ten Digital Force Gage; www.wagnerinstruments.com*).

PPTs will be evaluated at the trapezius muscles bilaterally and at the wrists bilaterally (four sites) by a trained and experienced RA. A 0.5 cm² probe covered with a rubberized pressure-transducing material will be applied twice to each site to measure PPTs. Mechanical force will be gradually increased until the subject verbally indicates to the tester that the pressure is “painful.” Temporal summation of mechanical pain will be assessed using weighted pinprick stimulators at each of the metacarpophalangeal joints of the middle fingers with a *Touch-Test Sensory Evaluator*

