(*www.ncmedical.com*).¹⁴ The subjects will be instructed to indicate which of the probes produced a painful sensation (usually the 128 or 256 mN gauge) and this stimulator will be used to apply a series of 10 sequential stimuli at the rate of 1 per second to the dorsum of the hand. The RA will ask the subjects to indicate their perceived level of painfulness of the first, fifth, and tenth stimulus. The degree of mechanical temporal summation will be determined by the increase in pain (as rated by the subject) between

the first and last stimulus. We and other groups have frequently employed these QST procedures in prior studies among patients with a broad array of musculoskeletal chronic pain conditions.^{11,12,18}

Patient Measures

Participants will complete measures recommended by the Initiative on Methods, Measures, and Pain Assessment in Clinical Trials (IMMPACT)¹⁹ as primary outcomes. All participants will be asked to complete a series of baseline questionnaires. Identical questionnaires will be mailed to the subjects for completion after 6 weeks and again after 3 months. All subjects will be supplied with self-addressed stamped envelopes to mail back their completed questionnaires. The following measures will be administered to the study patients: (1) The Brief Pain Inventory (BPI).^{20,21} It has been shown to have excellent reliability and validity among samples of chronic pain patients; (2) The Pain Disability Inventory (PDI).²² This is a 7-item questionnaire designed to assess activity-related disability in performing household chores, recreational and social activities, work-related and sexual activities, general activities of daily living, and life-supporting behavior. It has been shown to have excellent reliability and validity; (3) The Pain Catastrophizing Scale (PCS).^{23,24} This is an instrument that examines the propensity for recurring intrusive ruminating thoughts. Persons scoring high on this scale tend to magnify and amplify their pain and show signs of helplessness. It has good psychometric properties with adequate reliability and validity; (4) The Hospital Anxiety and Depression Scale (HADS).^{25,26} This is a valid and reliable measure of anxious and depressive symptoms over the past week. The HADS has been used extensively in

clinics to assess mood and has been shown to have an optimal balance between sensitivity and specificity.

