Once a week the subjects will be called by the RA and asked to rate their current progress on a 0=no pain/no interference to 10=worse possible pain/extreme interference on the following items: 1) current pain intensity, 2) average pain intensity, 3) pain interference on activities of daily living, social activities, outdoor and recreational activities, sleep, appetite, work ability, and 4) anxiety, depression and irritability from 0=stable mood to 10=worse possible mood. All questions were developed and standardized from a previous study.²⁷ All subjects will be asked about their current pain medications and all changes in prescription pain medications will be noted. Participants assigned to the Experimental group will be also asked which leg they used the hTENS on over the past week and all subjects will be given the opportunity to share any additional thoughts about the study.

At 3-month post-treatment all patients will be sent a packet of the baseline questionnaires to complete again and return by self-addressed stamped envelopes. Those in the Experimental group will be also asked to respond to a 14-item helpfulness questionnaire designed to investigate the perceived benefit of the hTENS. Those in the Control group will complete helpfulness questions only about the study and perceived helpfulness of the pain app. All items, which were developed in a prior study,¹⁸ and adapted from a previously validated measure,²⁸ will be rated on a 0 to 10 scale (e.g., not at all helpful to very helpful) and assessed helpfulness, bothersomeness, ease of use, how often they used the device, and whether the user was willing to use the hTENS in the future.

Statistical Analysis Plan

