The aim of this study is to establish the safety, efficacy, feasibility, and tolerability of the hfTENS device for use among chronic back pain patients. We will use an intent-to-treat analysis and all variables will be assessed using univariate and multivariate analyses to establish group differences at baseline and follow-up. Although this will be designed as a preliminary study, power calculations, as outlined by Cohen,²⁹ will be performed to determine the probability of detecting clinically significant differences between treatment groups in the primary area of measurement: pain intensity. These calculations will assume a two-tailed test and alpha level of 0.025 confirming the hypotheses that the Quell would be associated with general overall improvement (e.g., more pain relief). A more rigorous $p < 0.025$ significance level will be established rather than $p < 0.05$ because of the multiple observations. The power analyses is expected to reveal that a sample size of 60 subjects (30 per treatment group), gives the study a >80% probability of detecting a 1.5-point group difference on a 0-10 rating scale. Depending on the nature of the variables, chi-square, t-tests, and logistic regression analyses will be conducted. We also will examine and report on the qualitative responses of the participants in using the hfTENS. Group differences will be assessed using repeated measures ANOVA and preliminary mixed linear regression model analyses, as appropriate.

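### The SAP ranks none of its tests of group differences as primary and states no baseline adjustment; a baseline-adjusted comparison of pain at 3 months should be fixed as primary

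*Combined protocol and SAP*

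**What the plan says.** The Statistical Analysis Plan commits to intent-to-treat and then stays general: "We will use an intent-to-treat analysis and all variables will be assessed using univariate and multivariate analyses". It lists t-tests, chi-square and logistic regression according to the type of variable, and for group comparisons adds: "Group differences will be assessed using repeated measures ANOVA and preliminary mixed linear regression model analyses, as appropriate". It gives no order among these methods, no baseline adjustment, no primary time point and no missing-data rule. The outcome behind the power statement is given only as the "primary area of measurement: pain intensity".

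Pain is recorded in several ways. Patient Measures includes the BPI among the baseline questionnaires and says: "Identical questionnaires will be mailed to the subjects for completion after 6 weeks and again after 3 months". Later in the same section only the end-of-study mailing appears ("At 3-month post-treatment all patients will be sent a packet of the baseline questionnaires to complete again"), as it does in the Methods ("All subjects will be also asked to complete post-intervention mailed assessments after 3 months"). Weekly calls collect "1) current pain intensity, 2) average pain intensity", and the Methods also describe daily pain data from the app.

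**The concern.** Two things are at stake.

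- **Efficiency.** With two occasions, the group-by-time test of a repeated measures ANOVA is identical to a t-test on change scores. It subtracts the whole baseline value instead of weighting it by its correlation with follow-up. A baseline-adjusted comparison uses the same data and, with equal SDs, always has the smaller error variance. With 60 subjects that can matter.
- **Agreement with intent-to-treat.** If a classical ANOVA is run on complete cases over baseline, 6 weeks and 3 months, a subject who returned the 3-month form but not the 6-week form is left out, even though the end-of-study outcome is in hand.

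Because no method, pain item or time point is fixed, the choice could also be made after the data are seen.

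**Working it through.** **Inputs from the SAP:** difference 1.5 points, 30 per arm, two-sided alpha 0.025, power above 80%. **Assumed, because the documents give none:** SD, correlation r between occasions (0.3/0.5/0.7, equal for all pairs), and non-return rate.

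**1. The plan's own figure.** No SD is given, so the power claim can be neither confirmed nor refuted. Solving for the SD that gives exactly 80% with a noncentral t (58 df) yields SD = 1.843, a standardised difference of 1.5/1.843 = 0.81. The same t-test has power 93.9% at SD 1.5, 72.6% at SD 2.0 and 51.3% at SD 2.5. SD 1.843 is used below, so the t-test on 3-month scores alone has 80% by construction.

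**2. Complete data, baseline and 3 months.** The noncentrality is 1.5 / (S·√(2/30)), where S is:
- change score (two-level ANOVA): S = SD·√(2(1−r)), 58 df
- baseline-adjusted: S = SD·√(1−r²), 57 df

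| r | S, change | Power | S, adjusted | Power |
|---|---|---|---|---|
| 0.3 | 2.181 | 64.2% | 1.758 | 83.9% |
| 0.5 | 1.843 | 80.0% | 1.596 | 90.6% |
| 0.7 | 1.428 | 95.9% | 1.316 | 98.1% |

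A simulation with 8,000 replicates gave 64.5/79.7/95.6% and 83.1/89.9/97.9%. The variance ratio is 2(1−r)/(1−r²) = 2/(1+r) = 1.54/1.33/1.18. The two-level ANOVA on 60 subjects is therefore worth 60·(1+r)/2 = 39/45/51 baseline-adjusted subjects.

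With other SDs, change versus adjusted: at SD 1.5, 83/94/99.6% versus 96/98/99.9%; at SD 2.0, 56/73/92% versus 77/85/96%.

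**3. Narrower baseline spread.** Entry requires "average ≥ 4 on a 0-10 pain intensity scale", which may reduce the baseline SD. If it is 0.75 of the follow-up SD, the change variance is SD²·(1 + 0.75² − 2·0.75·r) = SD²·(1.5625 − 1.5r). Power of the change score becomes 75.2/88.1/98.1%. Adjusted power is unchanged at 83.9/90.6/98.1%, so the gain is 8.7/2.5/0.0 points, or about 9/3/0.

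**4. Complete data, three occasions.** For the group-by-time F test (2 and 116 df), λ = 30·Σ(δ−δ̄)² / (2·SD²(1−r)), where δ is the group difference at each occasion. If the full effect is present by 6 weeks (0, 1.5, 1.5), power is 69/85/98%. If half is present (0, 0.75, 1.5), it is 54/71/93%.

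**5. Incomplete returns, three occasions, complete cases.** Assume 10% non-return at each mailing, so 60·0.9 = 54 return the 3-month form.
- Independent misses: 60·0.9² = 48.6 complete; 54 − 48.6 = 5.4 responders dropped.
- Correlation 0.5 between misses: P(miss both) = 0.01 + 0.5·0.09 = 0.055; 60·(1 − 0.20 + 0.055) = 51.3 complete; 2.7 dropped.
- The same people miss both: 54 complete; none dropped.

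**6. Which replacement matters.** Baseline-adjusted power at 10% independent non-return:

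| Analysis set | r = 0.3 | r = 0.5 | r = 0.7 |
|---|---|---|---|
| Complete cases | 74.2% | 82.7% | 94.7% |
| All 3-month responders (ANCOVA) | 79.3% | 87.0% | 96.7% |
| Mixed model using 6-week data | 79.5% | 87.3% | 96.9% |

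Keeping all 3-month responders gives nearly all of the gain; the mixed model adds 0.2 to 0.3 points.

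**The case against.** Four points on the other side carry weight.

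- **A reader might infer that ANOVA is the main test and the mixed model is demoted.** The text does not say so. It joins the two without ranking them, the closing qualifier may apply to both, and the label attached to the mixed model may only echo the SAP's description of the whole study as preliminary. What stands is that nothing is primary.
- **A reader might infer that incomplete subjects will be deleted.** No section says this. The SAP states intent-to-treat and names a method that keeps partial data. The loss in step 5 is conditional on a complete-case ANOVA over three occasions, and two of the descriptions of follow-up mention only the 3-month mailing. Payment on return of forms, weekly calls and app reminders may also keep non-return low. Nor does any section propose an ANOVA over the weekly calls, so larger losses from that source are not a finding.
- **A reader might conclude that a mixed model is required.** Step 6 does not support that; ANCOVA on all 3-month responders performs almost identically.
- **The power loss is measured against a better method, not against the plan's target.** At r = 0.5 and 0.7 the two-level ANOVA still reaches 80% and 96%. Only at r = 0.3 does it fall short, and the gain can be nil (step 3 at r = 0.7). This is fair. It limits the size of the point, but the adjusted analysis is never worse in the settings computed and uses data already collected.

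The study's preliminary status does not remove the point, since the SAP states an efficacy aim, a hypothesis, an alpha and a power target.

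**Conclusion.** The concern holds in limited form. The SAP leaves several methods unranked and states no baseline adjustment for any of them. With complete data, choosing the two-level ANOVA instead of a baseline-adjusted comparison costs about 20/11/2 points of power at r = 0.3/0.5/0.7 (83.9 − 64.2, 90.6 − 80.0, 98.1 − 95.9), or about 9/3/0 points if the baseline spread is narrowed. Conflict with intent-to-treat arises only if a complete-case ANOVA spans three occasions; it then affects about 5 of 60 subjects at 10% independent non-return, and none if the misses fully overlap.

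The documents do not show that ANOVA is primary, that incomplete subjects will be excluded, or that the trial is underpowered. All sizes rest on an assumed SD, correlation and loss rate. Taking 3 months as the primary time is a reviewer's choice, but it matches the end of the study period. The change should be made; it is not a fatal flaw.

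**What to change.** Amend the SAP as follows.

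- **Primary analysis:** the device-minus-control difference at 3 months in one named BPI pain-intensity item, adjusted for the same item at baseline, with subjects analysed as randomised and every 3-month responder included.
- **Model:** ANCOVA. If the 6-week form is also used, a likelihood-based mixed model with baseline as covariate; state which follow-up times enter. The mixed model is valid if data are missing at random.
- **Secondary:** repeated measures ANOVA and the phone and app ratings. The questionnaire item is the better primary source because a matching baseline is collected, whereas no baseline call is described.
- **Sensitivity:** one analysis that covers randomised subjects with no follow-up value. With baseline as a covariate, neither ANCOVA nor the mixed model brings these subjects in.
- **Wording:** remove the open-ended qualifiers on the choice of model, and reconcile the descriptions of the mailings on whether a 6-week form is sent.

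The cost is SAP wording and slightly more analysis work. No new data are needed.
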